10.5.7 Stopping Rules

A comprehensive evaluation of data relevant to stopping rules will occur after enrollment of the first 10 participants. This study will be stopped at this time if: (1) the majority of investigators find that the harm to study participants outweighs the benefit of the scientific evidence to be accrued by continuing the trial; (2) new information from sources outside the trial provides definitive information that the intervention is effective or harmful; (3) any new information becomes available that necessitates stopping the trial; and (4) other situations occur that might warrant stopping the trial.

11 ADMINISTRATIVE, ETHICAL, AND REGULATORY CONSIDERATIONS

The investigator is responsible for presenting the risks and benefits of study participation to the subject's parent/guardian or legally authorized representative in simple terms using the informed consent document. The investigator will ensure that written informed consent is obtained from each parent/guardian or legally authorized representative by obtaining the appropriate signatures and dates on the informed consent document before the performance of protocol evaluations or procedures.

11.1 Ethical Review

The sponsor will obtain documentation by the applicable local IRB/IEC of approval of the protocol and the informed consent document before the study may begin at the investigative site(s). The name and address of the reviewing IRB/IEC are provided in the investigator file.

The sponsor will supply the following to the investigative site's IRB/IEC:

- Protocol and amendments.
- Informed consent document and updates.
- Relevant curricula vitae, if required.
- Required safety and SAE reports.
- Any additional submissions required by the site's IRB/IEC.

The sponsor will retain the following documentation, if applicable:

- The IRB/IEC periodic (e.g., quarterly, annual) re-approval of the protocol.
- The IRB/IEC approvals of any amendments to the protocol or revisions to the informed consent document.
- The IRB/IEC receipt of safety and SAE reports, as appropriate.

11.2 Regulatory Considerations

This study will be conducted in accordance with the protocol and ethical principles stated in the 2013 version of the Declaration of Helsinki or the applicable guidelines on GCP, and all applicable federal, state, and local laws, rules, and regulations.

All data recorded in the CRF for subjects participating in this study will be transcribed from medical records. After reading the protocol, the investigator will sign the protocol signature page and return it to the sponsor or designee.

11.2.1 Investigator Information

The contact information and qualifications of the principal investigator and subinvestigators, and name and address of the research facilities are included in the investigator file.

11.2.2 Protocol Amendments and Study Termination

The sponsor will initiate changes to the protocol as necessary (with the exception of changes to eliminate an immediate hazard to a study subject) and seek approval by the IRB/IEC prior to implementing. The investigator is responsible for enrolling subjects who have met protocol eligibility criteria. Protocol violations must be reported to the local IRB in accordance with IRB policies. The sponsor may terminate the study at any time. The IRB must be advised in writing of study completion or early termination.

11.2.3 Study Documentation, Privacy, and Records Retention

Government agency regulations and directives require that all study documentation pertaining to the conduct of a clinical trial must be retained by the investigator for a minimum of 5 years (or longer if required by the local IRB/IEC).

To protect the safety of participants in the study and to ensure accurate, complete, and reliable data, the investigator will keep records of laboratory tests, clinical notes, and subject medical records in the subject files as original source documents for the study. If requested, the investigator will provide the applicable regulatory agencies and applicable IRB/IEC with direct access to original source documents.

Records containing subject medical information must be handled in accordance with the requirements of the Health Insurance Portability and Accountability Act (HIPAA) Privacy Rule and consistent with the terms of the subject authorization contained in the informed consent document for the study. Care should be taken to ensure that such records are not shared with any person or for any purpose not contemplated by the informed consent document. Furthermore, CRFs and other documents should be completed in strict accordance with the instructions provided by the sponsor-investigator, including the instructions regarding the coding of subject identities.

11.3 Study Finances

This study is financed through Global Good/Intellectual Ventures. Global Good/Intellectual Ventures holds Public Liability ("negligent harm") and Clinical Trial ("non-negligent harm") insurance policies, which apply to this trial.

11.4 Publications

Neither the complete nor any part of the results of the study carried out under this protocol, nor any of the information provided by the sponsor for the purposes of performing the study, will be published or passed on to any third party without the consent of the study sponsor. Any investigator involved with this study is obligated to provide the sponsor with complete test results and all data derived from the study.

APPENDIX A: SCHEDULE OF EVENTS

Activity	Screening	Period 0 (Baseline)	Period 1 (1 hr)	Period 2 (1 hr)
		Group A	Nasal reservoir + nasal cannula	nasal cannula
		Group B	Nasal cannula	Nasal reservoir + nasal cannula
Recruitment/Informed Consent	X			
Medical history	X			
Physical examination	X		X (end of period)	X (end of period)
Severe pneumonia (based on WHO criteria) ^a	X			
SpO ₂ 85-93% on room air (pulse oximetry)	X			
Capillary blood gas with lactate	X		X (end of period)	X (end of period)
Signs of inflammation in children that can kill (SICK) score	X		X (end of period)	X (end of period)
Hemoglobin rapid test	X			
Complete blood count (hematology panel)	X			
Malaria rapid diagnostic test	X			
Blood glucose (point of care)	X			
Comprehensive metabolic panel ^b	X			
Determine nasal reservoir size		X d		
SpO ₂ >90% on oxygen (pulse oximetry)		X		
Vital signs ^c		X f	record values every 15 min	
Record concomitant medication information		X	X	X
Continuous transdermal end-tidal CO ₂ monitoring			record values	s every 15 min
Continuous SpO ₂ monitoring (during supplemental O ₂)			record values every 15 min	
Record oxygen flow (L/min)			record values	s every 15 min
Record adverse event information			X	X

- a. Severe pneumonia based on World Health Organization criteria (Appendix B).
- b. Comprehensive metabolic panel will be obtained only if indicated as part of standard of care.
- c. Vitals signs: blood pressure, respiratory rate, heart rate, and temperature. Obtain at baseline (pretreatment) and every 15 minutes from the beginning of Period 1 through end of Period 2. Any values obtained during Screening period may be used as Baseline values.
- d. Patients with a body weight of 8-13 kg will receive treatment with a small 30 ml mask and patients with a body weight of 14-26 kg will receive treatment with a large 50 ml mask.

APPENDIX B:

World Health Organization (WHO) Definition of Severe Pneumonia

(World Health Organization 2013)

Sign or symptom	Classification	Treatment
Cough or difficulty in	Severe	 Admit to hospital.
breathing with:	pneumonia	 Give oxygen if saturation
 Oxygen saturation < 90% or central cyanosis 		< 90%. – Manage airway as
Severe respiratory distress		appropriate.
(e.g. grunting, very severe chest indrawing)		 Give recommended antibiotic.
Signs of pneumonia with a general danger sign (inability to breastfeed or drink, lethargy or reduced level of consciousness, convulsions)		 Treat high fever if present.

APPENDIX C:

SIGNS OF INFLAMMATION IN CHILDREN THAT CAN KILL (SICK) SCORE

(from Kumar et al., 2003)

Table 1: Scoring of abnormal clinical variables[7]

Variable	Abnormal range	
Temperature	>38°C < 36°C	
Heart rate	Infant >160 per minute	
	Child >150 per minute	
Respiratory rate	Infant >60 per minute	
	Child >50 per minute	
Systolic blood pressure	Infant <65 mm Hg	
	Child <75 mm Hg	
SpO ₂	<90%	
Capillary refill time	≥3 seconds	
A Alert	Anyone except A	
V Responds to voice		
P Responds to pain		
U Unresponsive		
The state of the s		

Based on SIRS and APLS[8,9]

Table 2: Weight (Regression coefficient) for each variable* developed in previous study^[7]

Variable	Weight
Heart rate	0.2
Respiratory rate	0.4
Blood pressure (systolic)	1.2
Temperature	1.2
SpO ₂	1.4
Capillary filling time	1.2
AVPU	2.0
Age (months)	
≥ 60	0.0
≥ 12 to <60	0.3
\geq 1 to $<$ 12	1.0
<1	2.2

^{*}Based on multiple logistic regression analysis

Appendix F: Serious Adverse Event Reporting Form

Nasa	ocol Title: A Feasibility Study Evaluating a Novel Mask (Nasal Reservoir Cannula) Plus Standard al Cannula vs Standard Nasal Cannula Alone for Supplemental Oxygen Delivery in the Treatment of pitalized Pediatric Patients with Hypoxemia Due to Severe Pneumonia
	Pt_IP number: Study ID number:
1.	SAE Onset Date: (dd/mm/yyyy)
2.	SAE Stop Date:(dd/mm/yyyy)
3.	Location of serious adverse event:
4.	Was this an unexpected adverse event? Yes No
5.	Brief description of participant(s) with no personal identifiers: Sex: F M Age:
6.	Brief description of the nature of the serious adverse event (attach description if more space needed):
7.	Category of the serious adverse event:
	☐ death – date//(dd/mmm/yyyy) ☐ congenital anomaly / birth defect ☐ life-threatening ☐ required intervention to prevent ☐ hospitalization-initial or prolonged permanent impairment ☐ disability / incapacity ☐ other:
8.	Intervention type:
	Medication or Nutritional Supplement: specify
	Device: Specify:
	Surgery: Specify:
	Behavioral/Life Style: Specify:

9.	Relationship of event to intervention:
	Unrelated (clearly not related to the intervention) Possible (may be related to intervention) Definite (clearly related to intervention)
10.	Was study intervention discontinued due to event? Yes No
11.	What medications or other steps were taken to treat serious adverse event?
12.	List any relevant tests, laboratory data, history, including preexisting medical conditions
13.	Type of report:
	☐ Initial ☐ Follow-up ☐ Final
	Signature of Principal Investigator: Date:

APPENDIX G LABORATORY REFERENCE RANGES

iSTAT CG-	4 reportable ranges	
Lab Value	Reportable Range (units)	Lowest allowable values in data base
pН	6.5 - 8.2	6.4
BE	-30-+30mmol/L	-29
pCO ₂	5 – 130 (mm Hg)	4.9
pO ₂	5 – 800 (mm Hg)	4.9
HCO ₃	1.0 - 85.0 (mmol/L)	0.9
Total CO ₂	5 – 50 (mmol/L)	4.9
Lactate	0.30 - 20.0 (mmol/	0.2

iSTAT Chem8	+ reportable ranges	
Lab Value	Reportable Range (Conventional Units)	Lowest Values allowed in data base
Sodium	100-180(mmol/L)	
Potassium	2.0-9.0(mmol/L)	
Chloride	65-140(mmol/L)	
Ionized Calcium	0.25-2.50(mmol/L)	0,2
Glucose	1.11-38.89(mmol/L)	1.0
BUN	1.07-49.98(mmol/L)	1.0
Creatinine	17.68-1768(μmol/L)	17
Anion Gap	-10-99(mmol/L)	-9.9
Total CO2	5-50(mmolL)	4.9
Hemoglobin	3.4-25.5(g/dL)	3.3
Hematocrit	10-75(% PCV)	9.9

AReportable Ranges for the ACutrend Lactometer, Glucometer and Haemocue

Lab Value	Point of Care Equipment	Reportable Range	Lowest value in data base
Lactate	ACutrend Lactometer	0.8 -22 Mmol/L	0.7
GLYCOSE	GhucomeTER	1.1-33.3 Mars//L	1.D
HAEMOGLOBIN	HAEMOCUE 301	0-25.69/1	1.0

APPENDIX H Data and Safety Monitoring Plan

A. Confidentiality

- 1. Protection of Subject Privacy— During this study, a physical examination and blood tests will be performed. Data will be kept in strict confidence. No information will be given to anyone without permission from the parents of the participant. This statement guarantees confidentiality. Confidentiality is assured by use of study identification numbers. All clinical and laboratory data will be identified only by the study identification number unique to the subject. No participant specimens will be stored for future use.
- 2. Database Protection— The database is secured with password protection. The informatics manager receives only coded information, which is entered into the database under those identification codes. Electronic communication with outside collaborators involves only unidentifiable information.
- 3. Confidentiality during Adverse Event Reporting— Adverse event reports will not include subject-identifiable material. Each will include the study identification number only.

B. Adverse Event Information

1. Definitions- An adverse event (AE) will be defined as **any** new unfavorable or unintended sign, symptom, or disease or change of an existing condition, which occurs during or within 1 hour after treatment, whether or not considered treatment-related. If clinically significant laboratory values lead to or are associated with clinical symptom(s), the diagnosis should be reported as an AE. Lack of treatment effect is not an adverse event in clinical trials because the purpose of the clinical trial is to establish (or evaluate for) a treatment effect.

A serious adverse event (SAE) is defined as an AE that suggests a significant hazard or side effect, regardless of the relationship to study treatment. An SAE includes, but may not be limited to, any event that:

- Results in death.
- Is life-threatening. This definition implies that the subject, in the view of the investigator, is at immediate risk of death from the event. It does not include an event that, had it occurred in a more serious form, might have caused death.
- Requires inpatient hospitalization or prolongs existing hospitalization.
- Results in persistent or significant disability/incapacity.
- 2. Classification of AE Severity AEs will be labeled according to severity, which is based on their impact on the patient, per this Event Grading Scale:
 - Grade 1 Mild: Transient of mild discomfort; no limitation in activity; no medical intervention/therapy required.
 - Grade 2 Moderate: Mild to moderate limitation in activity some assistance may be needed; no medical intervention/therapy required.

- Grade 3 Severe: Marked limitation in activity, some assistance usually required; medical intervention/therapy required, hospitalizations possible.
- Grade 4 Life-threatening: Extreme limitation in activity, significant medical intervention/therapy required.
- 3. AE Attribution Scale— AEs will be categorized according to the likelihood that they are related to the study intervention. The relationship of an AE/SAE to the study treatment or procedure should be based on the judgment of the investigator and assessed using the following the guidelines:
 - Definitely: Previously known toxicity of study treatment or procedure; or an event that follows a reasonable temporal sequence from administration of the study treatment or procedure; that follows a known or expected response pattern to the suspected study treatment or procedure; that is confirmed by stopping or reducing the dosage of the study treatment or procedure; and that is not explained by any other reasonable hypothesis.
 - Probably: An event that follows a reasonable temporal sequence from administration of the study treatment or procedure; that follows a known or expected response pattern to the suspected study treatment or procedure; that is confirmed by stopping or reducing the dosage of the study treatment or procedure; and that is unlikely to be explained by the known characteristics of the subject's clinical state or by other interventions.
 - Possibly: An event that follows a reasonable temporal sequence from administration of the study treatment or procedure; that follows a known or expected response pattern to that suspected of study treatment or procedure; but that could readily have been produced by a number of other factors.
 - Unrelated: An event that can be determined with certainty to have no relationship to the study treatment or procedure.
- 4. Expected Risks— Expected risks to the subjects are mild discomfort due to blood draws. These risks are considered to be minimal and are addressed in the protocol and consent form. There is minimal risk associated with the device.

This study involves a newly developed non-invasive investigational device, a nasal reservoir cannula that can significantly improve access to effective and safe oxygen therapy for children with respiratory distress. This device is an add on approach to be used in conjunction with a standard nasal cannula with prongs which will allow a more rational use of oxygen and in turn better adjustment of treatment to patient needs. The device does not replace the standard method of care of oxygen delivery via nasal cannula; therefore, it does not present any new or additional potential for serious risk to health, safety or welfare of subjects.

Potential risks might be that the subject develops a condition or begins a therapy that would have excluded entry into the study such as hypercapnia, requiring intubation or non-invasive or invasive positive—pressure ventilation, or suspected or known pneumothorax. It is important to note that these potential risks are independent of the investigational device

and might be a potential risk during any type of oxygen therapy. The study investigators have years of experience providing clinical care for children with respiratory problems and conducting clinical research in children.

5. SAE Reporting- SAEs that are unanticipated, serious (grades 3 and 4), and/or possibly related to the study intervention must be reported to the sponsor by telephone within 24 hours of the investigator becoming aware of the event. In addition, a SAE reporting form must be completed by the site PI and faxed to the sponsor within 24 hours of the PI becoming aware of the event. In addition, the site PI must report SAEs to the Mulago Research and Ethics Committee (MREC) in accordance with the MREC's standard operating procedures and policies. Anticipated SAEs or those unrelated to the study intervention will be reported to the same individuals/entities in accordance with requirements.

Sponsor phone numbers include: [name]: [name] or [name] [name] (United States-based).

Investigator phone numbers include: [name] [name] (Uganda-based.

If abnormal lab values are discovered during the study, the site PI will be notified and will address this issue as early as possible. Clinically significant laboratory abnormalities (see protocol Appendix F), which are new or worsen during the study period, will be recorded and reported as AEs or SAEs as appropriate based on the above definitions. Abnormal lab values will be reported as AEs only when the site PI deems them to be clinically significant. For clinically significant laboratory abnormalities, a member of the local research team (site PI, study pediatrician, or study nurse) will provide a brief report on how the abnormal value was managed.

C. Data Quality and Safety Monitoring and Review Plan

- 1. Data Quality and Management
- a. Description of Plan for Data Quality and Management— The study coordinator will review all data collection forms on an ongoing basis for data completeness and accuracy. A statement reflecting the results of the review will be sent to the sponsor at 6-month intervals. Data quality will be assessed using measures such as time from study visit to data entry, time to resolution of data queries, number of missing forms, and proportion of all study variables queried. Guidelines for concern regarding these measures are outlined below:

Measure	Goal Value	Acceptable Value
Time from visit to data entry	<1 week	<2 weeks
Time to resolution of queries	<2 weeks	<3 weeks
Percentage of missing fields on data collection forms	0	<5%

b. Frequency of Review—The frequency of data review depends according to the type of data and is summarized in the following table.

Data Type	Frequency of review	Reviewer
Subject accrual (adherence to	Every 2 weeks	Study pediatrician/coordinator and
eligibility criteria)		site PI
Protocol adherence	Monthly	Study pediatrician/coordinator and
		site PI
Adverse event rates	Monthly	Study pediatrician/coordinator and
	-	site PI
Evaluation of data relevant to	After 10 participants	Study pediatrician/coordinator,
stopping rules	have been enrolled	site PI, and UCSF PI

- 2. Subject Accrual and Protocol Adherence
- a. Measurement and reporting of subject accrual, adherence to inclusion/exclusion criteria—Review of the rate of subject accrual and adherence to inclusion/exclusion criteria will occur every 2 weeks.
- b. Measurement and reporting of protocol adherence— Data on protocol adherence will be reviewed monthly.
- 3. Safety Monitoring- Safety evaluations will include collection of AE, physical examination, vital sign, and clinical laboratory data. Safety evaluation will involve the collection of data from:
 - Continuous transdermal end-tidal carbon dioxide (CO₂) monitoring
 - Capillary blood gases (PO₂, PCO₂, pH, base excess, lactate)
 - Peripheral blood oxygen saturation (SpO₂)

Additional laboratory tests at the time of screening will include rapid hemoglobin, malaria rapid test, blood glucose (point of care), and complete blood count (CBC), which may include hemoglobin, hematocrit, erythrocyte or red blood cell count (RBC), mean cell volume (MCV), segmented neutrophils, juvenile neutrophils, lymphocytes, monocytes, eosinophils, basophils, platelets, cell morphology, reticulocyte count. The decision to obtain metabolic panel in subjects will be based on local standard of care for patients with respiratory distress, but may include evaluation of:

- Metabolic panel: Serum concentrations of sodium, potassium, chloride, total bilirubin, alkaline phosphatase, alanine transaminase (ALT), aspartate transaminase (AST), blood urea nitrogen (BUN), creatinine, glucose, total protein, albumin.
- 4. Stopping Rules— An individual subject will be withdrawn from the study if he or she develops a condition or begins a therapy during the study period that would have excluded entry into the study (e.g., hypercapnia, acidosis, hemodynamic instability, requirement of intubation or positive pressure ventilation, $SpO_2 < 90\%$ on oxygen, SICK score > 2.4). In addition, a comprehensive evaluation of data relevant to stopping rules will occur after enrollment of the first 10 participants. This study will be stopped at this time if: (1) the majority of investigators find that the harm to study participants outweighs the benefit of the scientific evidence to be accrued by continuing the trial; (2) new information from sources outside the trial provides definitive information that the intervention is effective or

harmful; (3) any new information becomes available that necessitates stopping the trial; and (4) other situations occur that might warrant stopping the trial.

D. Progress Reports

Progress reports summarizing data quality, protocol adherence, and AEs will be prepared by the study pediatrician/coordinator and provided to the PI and sponsor monthly for review. After 10 patients have been enrolled, an additional report will address (1) whether AE rates are consistent with pre-study assumptions; (2) reason for dropouts; (3) whether all participants met entry criteria; (4) whether continuation of the study is justified on the basis that additional data are needed to accomplish the stated aims; and (5) conditions whereby the study might be terminated prematurely. This report will be signed by the PIs and forwarded to the MREC and the sponsor.

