10.5.6 Safety Analyses

Treatment-emergent AEs are defined as AEs occurring after the first initiation of treatment until completion of treatment. Duration of treatment will be summarized by treatment group. The incidence of all reported AEs and treatment-related AEs will be tabulated by treatment group. AEs will be classified by system organ class and verbatim term.

AEs will be listed and summarized by treatment group, verbatim term, severity, seriousness, and relationship to study drug. In the event of multiple occurrences of the same AE with the same verbatim term in one subject, the AE will be counted once as the worst occurrence. The incidence of AEs will be tabulated by system organ class and

treatment group. AEs leading to premature discontinuation of study drug or withdrawal from the study will be summarized and listed in the same manner.

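### The Appendix H severity grades do not cover treated mild or moderate events or deaths, and B.5 conflicts with Section 8.1.3 on serious events and their reporting

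*Protocol*

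**What the plan says.** Appendix H, B.2 applies one scale to all adverse events: "AEs will be labeled according to severity, which is based on their impact on the patient, per this Event Grading Scale". Each of its four grades joins an activity level to a treatment level. The lowest, for mild events, admits neither a restriction on activity nor any treatment. The second, for moderate events, is worded "Mild to moderate limitation in activity some assistance may be needed; no medical intervention/therapy required". Treatment enters only at the third, severe level, where it goes with a marked restriction and a possible hospital stay. The fourth, life-threatening level pairs an extreme restriction with significant treatment.

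The scale ends there. No rule says whether an event must meet all the descriptors of a grade or only one.

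Section 8.1.1 has every AE rated for intensity, seriousness and causality. Section 10.5.6 then reports these attributes separately: "AEs will be listed and summarized by treatment group, verbatim term, severity, seriousness, and relationship to study drug". If a child has the same event more than once, 10.5.6 keeps only the worst instance.

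Seriousness is defined elsewhere. Section 8.1.3 and Appendix H, B.1 define an SAE by hazard and outcome, with death first on the list and no mention of grade. Section 8.1.3 requires any such SAE to reach the sponsor within 24 hours. Appendix H, B.5 words the 24-hour duty differently: "SAEs that are unanticipated, serious (grades 3 and 4), and/or possibly related to the study intervention must be reported". It closes by sending anticipated or unrelated SAEs to the same recipients with no time limit stated.

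**The concern.** A severity scale has to give each event one grade. Here the two axes, activity and treatment, move together in the definitions but need not do so in a child. A clinically significant laboratory abnormality that is treated without limiting activity is an example. Section 8.1.4 makes it reportable, and B.5 asks for a brief account of how it was managed, yet no grade describes it.

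Two raters could reasonably record different grades for the same event, and in an open-label study the rater knows which device is in use. The rule that keeps the worst instance needs a complete ordering, which the scale does not give. Grades are recorded as events occur, so a later analysis plan cannot recover them if the scale was ambiguous.

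The second issue is that B.5 mixes severity with seriousness, while Section 10.5.6 treats them as separate attributes. B.5 also sets a different scope for 24-hour reporting from 8.1.3.

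**Working it through.** The protocol gives no figure to reproduce here, so the check is an enumeration.

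**Inputs**, all from Appendix H, B.2: four activity levels (none, mild to moderate, marked, extreme) and whether therapy is required (no, yes). This gives 4 × 2 = 8 combinations. Each is graded in two ways. On the literal reading, both descriptors of a grade must be met. On the worst-descriptor reading, the grade is the higher of the two taken separately: activity scores 1, 2, 3 or 4; no therapy scores 1; therapy scores 3, the first grade that allows it.

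| Activity limitation | Therapy | Literal | Worst descriptor |
|---|---|---|---|
| none | no | 1 | max(1, 1) = 1 |
| none | yes | no grade | max(1, 3) = 3 |
| mild to moderate | no | 2 | max(2, 1) = 2 |
| mild to moderate | yes | no grade | max(2, 3) = 3 |
| marked | no | no grade | max(3, 1) = 3 |
| marked | yes | 3 | max(3, 3) = 3 |
| extreme | no | no grade | max(4, 1) = 4 |
| extreme | yes | 4 | max(4, 3) = 4 |

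On the literal reading, 8 − 4 = 4 of 8 combinations have no grade. On the worst-descriptor reading all 8 can be graded, but both treated combinations below marked limitation become Grade 3. On neither reading can a treated mild or moderate event be Grade 1 or 2. Death matches none of the four definitions as written.

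The count depends on how treatment is split. With three levels (none, some, significant) there are 4 × 3 = 12 profiles. Five fit a grade if marked limitation with significant treatment counts as Grade 3, which leaves 7 without one. The treated mild and moderate profiles are ungraded under either split.

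**B.5 against 8.1.3.** In 8.1.3, any SAE meeting the outcome definition is due within 24 hours. In B.5, the 24-hour sentence selects SAEs that are unanticipated, of grade 3 or 4, or possibly related, joined by and/or; a later sentence gives anticipated or unrelated SAEs no time limit. An anticipated, unrelated Grade 4 SAE falls under both B.5 sentences. An anticipated, unrelated death has no grade, so read literally it falls only under the untimed sentence, yet 8.1.3 requires 24 hours.

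**The case against.** The strongest reply is that little depends on the grade. This is a descriptive feasibility study of up to 20 children over about two hours, with significance tests only exploratory. SpO₂ and CO₂ are recorded every 15 minutes and are safety variables in their own right (10.3). Hypercapnia and low SpO₂ on oxygen lead to withdrawal (8.1.5), and withdrawals are listed with reasons (10.5.3). Intubation, positive-pressure ventilation or pneumothorax would plausibly reach Grade 3 or 4. None of the listed stopping criteria in 10.5.7 uses a grade. All of this stands, and it confines the gap to lesser events that need some treatment.

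It can also be said that B.2 bases severity on impact on the patient, which gives the rater a guiding principle. That helps only in part: a rater who follows it to Grade 1 or 2 for a treated event must disregard the no-treatment clause in both grades.

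Three stronger readings are tempting, and the protocol does not support them.

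- A reader might infer that B.5 turns a treated minor event into a serious one. The B.5 sentence concerns events that are already SAEs. An event meeting no SAE criterion never enters it.
- A reader might infer that such an event is both ungraded and serious under B.5. These belong to different readings: if it has no grade, the grade parenthesis cannot reach it, and only the worst-descriptor reading takes it to Grade 3.
- A reader might infer that deaths are lost. Death is the first SAE criterion in 8.1.3 and B.1, and the SAE form has a box and date for it. Only the severity label is missing.

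**Conclusion.** The point holds in limited form. The B.2 grades are not exhaustive: a mild or moderate event needing treatment is either ungradable or labelled Severe, and a fatal event has no grade. On a literal two-level reading the gap is 4 of 8 combinations. That counts definitions, not events: the cells are not equally likely, and marked or extreme limitation without treatment is hardly plausible. With no event rates given, the number of affected events cannot be estimated.

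The consequence falls on the severity tabulation in 10.5.6 and on its handling of repeated events. With at most 20 children, one regraded event in one child moves an all-children percentage by 1/20 = 5 points. Which events count as SAEs does not change.

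Separately, B.5 and 8.1.3 disagree on the scope of 24-hour SAE reporting, and the B.5 parenthesis attaches a severity grade to seriousness. These texts must be reconciled. The correction is worth making before enrolment because it is cheap and the grades cannot be repaired afterwards.

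**What to change.** In Appendix H, B.2:

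1. State that an AE takes the highest grade for which any one criterion is met.
2. Let Grade 2 include minor intervention.
3. Limit the treatment criterion of Grade 3 to more than minor intervention. Without this, the first rule still pushes every treated event to at least Grade 3.
4. Add a fatal grade, or state that fatal events are tabulated separately.

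A short definition of minor intervention is needed so that the grades stay distinct.

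In Appendix H, B.5: delete the parenthesis naming grades 3 and 4. Reword the sentence, since what remains would describe SAEs as serious. Reconcile the 24-hour scope with 8.1.3, so that seriousness and reporting follow one outcome-based definition.

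The cost is a few words in Appendix H and in any AE form that repeats the scale, with no new data. The one small downside is that some treated minor events move from Grade 3 to Grade 2.
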